### 7.1.3.2 Incomplete Dates

If the date of onset is incomplete, then the month and year of onset (or year alone if month is not recorded) determines whether the event is treatment-emergent. The event is treatment-emergent if the month and year of onset (or year of onset) of the event is:

- The same as or after the month and year (or year) of the first dose of study drug, and
- The same as or before the month and year (or year) of the date of the last visit.

### 7.1.4 Adverse Event Severity

The investigator will grade the severity of the AEs as Grades 1, 2, 3, 4, or 5 based on the National Cancer Institute (NCI) Common Terminology Criteria for Adverse Events (CTCAE), version 4.03.

### 7.1.5 Relationship of Adverse Events to Study Drug

Association or relatedness to the study medication will be graded by the investigator as either probably, possibly, unlikely, or unrelated according to criteria specified in the study protocol.

### 7.1.6 Serious Adverse Events

As defined in the protocol and captured on the CRF, an SAE is an adverse event that results in any of the following:

- Death;
- A life-threatening adverse drug experience;
- Inpatient hospitalization or prolongation of existing hospitalization;
- Results in persistent or significant incapacity or substantial disruption of the ability to conduct normal life functions;
- Results in a congenital anomaly or birth defect in an offspring of a patient taking study drug;
- Is an important medical event.

#### 7.1.6.1 Summaries of Adverse Events

Treatment-emergent AEs will be summarized by treatment at onset of the AEs. For each treatment, SOC, and PT, the number and percentage of patients reporting an event will be calculated. In summary tables, SOC will be presented alphabetically and events within SOC will be presented by decreasing frequency count based on the number of events in the total group.

Summary tables (number and percentage of patients) of AEs (by SOC and PT) will be provided by treatment as follows:

- All treatment-emergent AEs
- All treatment-emergent related AEs (probably or possibly related)
- All treatment-emergent AEs by severity
- All treatment-emergent serious adverse events (including deaths)
- All treatment-emergent adverse events leading to discontinuation of study drug

Listings will be provided showing:

- All AEs

- Serious adverse events (including deaths)
- AEs leading to discontinuation of study drug

#### 7.1.6.2 Additional Analysis of Adverse Events

No additional analysis of AEs is planned.

## 7.2 Clinical Laboratory Evaluations

Laboratory data will be summarized at baseline and at each time point by treatment. Only values obtained at scheduled assessment times will be included in by-visit summary statistics. When appropriate, change from baseline to worst post-baseline (including unscheduled visits) value will be summarized. Specific assessment times are given in [Appendix 1](#) of this analysis plan.

Continuous laboratory data results which are less than the lower limit of quantification or above the upper limit of quantification will be imputed to the value of the lower or upper limit plus or minus one significant digit, respectively (e.g., if the result of a continuous laboratory test is < 20, a value of 19 will be assigned). A baseline value is defined as the last available measurement obtained prior to administration of the first dose. If multiple values for a given lab test exist for a particular day, the last one drawn will be used for summarization.

### 7.2.1 General Considerations for Analyses of Laboratory Data

Clinical laboratory results will be provided by a central lab. Clinical laboratory test results, including results from hematology, chemistry and urinalysis will be listed by patient.

### 7.2.2 Summaries of Laboratory Results

Selected laboratory evaluations and change from baseline will be summarized by treatment, laboratory category (hematology, chemistry), test, and study visit using continuous statistics. Laboratory tests to be summarized are provided in [Appendix 2](#).

Due to the nature of urinalysis parameters, summaries of continuous statistics will not be provided.

### 7.2.3 Laboratory Abnormalities

Laboratory results are not captured on the CRF. All flags with respect to normal or abnormal results will be identified by the central lab.

### 7.2.4 Treatment-Emergent Abnormalities

Treatment-emergent laboratory abnormalities are defined as values with any shift from a normal at baseline (Day 1) to abnormal at any time post-baseline up to and including the last dosing date. Additionally, a shift from a low non-normal baseline value to a high non-normal post baseline value (and vice versa) will also be considered treatment emergent. If the relevant baseline laboratory values are missing, then any abnormality will be considered treatment emergent.

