^r Radiation dermatitis assessments must be performed PRIOR to initiation of that day's radiation treatment, and only by a trained evaluator. If radiation treatment is delayed or extended, dermatitis assessments should be performed weekly until the end of radiation treatment.

^s The Skindex-16 must be completed prior to initiation of that day's radiation treatment.

^t Screening lab assessments (described in Section 9.8 for [chemistry](#), [hematology](#), [urinalysis](#), and [serum pregnancy tests](#)) should be drawn ≤ 14 days prior to randomization in order to have current values for inclusion/exclusion assessment.

^u A single PK collection will be obtained on Visit 3, Visit 6, Visit 9, Visit 11 and Visit 12. If patients are to receive a morning radiation treatment on any of these visits, the PK sample should be drawn after RTA 408 Lotion or Vehicle Lotion application, which occurs after the completion of radiation treatment. If patients are to receive an afternoon radiation treatment on any of these visits, the PK sample should be drawn after the radiation treatment.

^v Optional photographs may be collected at Sponsor-qualified sites. On Day 1 of radiation treatment and the last day of radiation treatment, photographs must be collected prior to radiation treatment.

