8. SELECTION AND WITHDRAWAL OF PATIENTS

8.1. Patient Inclusion Criteria

All patients must meet all of the following criteria to be included in the study:

1. Adult female patients (18 to 80 years of age, inclusive);
2. Patients diagnosed with ductal carcinoma in situ or non-inflammatory breast adenocarcinoma who have been referred for post-operative radiotherapy and have had no prior radiation treatment to that breast;
3. Patients planning to undergo 3D conformal radiation therapy to the whole breast (as part of breast-conservation therapy / lumpectomy) or chest wall (as part of post-mastectomy irradiation), with or without treatment of regional lymph nodes (i.e., axillary, supraclavicular, or internal mammary), using one of the following treatment schedules:
 - a. 45 – 50.4 Gy in 1.8 Gy per day, in addition to a mandatory 10-16 Gy boost
 - b. 46 – 50 Gy in 2 Gy per day, in addition to a mandatory 10-16 Gy boost;
4. Patients who received breast-conservation therapy / lumpectomy must be receiving $\geq 107\%$ of the total radiation dose (calculated from the total radiation dose including boost) to any portion of the breast, based on radiation inhomogeneity, **and/or** have a breast volume ≥ 1200 cc;
5. Female patients of childbearing potential who are willing to practice methods of birth control from screening through 1 month after applying the final dose of study drug;
6. Female patients of childbearing potential who are non-pregnant, non-lactating and have a negative pregnancy test result prior to enrollment in the study;
7. Patients willing and able to give written informed consent for study participation;
8. Patients willing and able to cooperate with all aspects of the protocol;
9. Patients for which at least 14 days have elapsed since breast conservation surgery, mastectomy surgery and/or chemotherapy prior to randomization;
10. Have adequate hematologic and organ function at screening as follows:
 - a. Hematologic: Absolute neutrophil count $\geq 1.5 \times 10^3$ / μ L, platelets $> 100 \times 10^9$ /L, hemoglobin ≥ 9 g/dL;
 - b. Hepatic: total bilirubin ≤ 1.5 times (X) upper limit of normal (ULN), ALT and AST \leq ULN;
 - c. Renal: serum creatinine ≤ 1.5 mg/dL

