8.4.1. Patient Discontinuation Criteria

Discontinuation refers to a patient stopping administration of study drug. Reasons for study drug discontinuation include the following:

- Occurrence of an adverse event (AE) or change in medical status that leads the investigator to be concerned about the patient's welfare
- Noncompliance with study procedures
- Pregnancy during the study
- Investigator unblinding of patient

Patients who are discontinued from study drug should still attend all study visits and undergo all study assessments, if possible.

The CTCAE version 4.03 will be used to define patient stopping criteria for systemic adverse events, except where related to transaminase laboratory values. The criteria for a stopping criteria for adverse events related to transaminase laboratory values will be defined using the FDA Guidance for Industry titled "Drug-Induced Liver Injury: Premarketing Clinical Evaluation" (July 2009) rather than CTCAE.

The determination stopping criteria will be defined in each patient as all toxicity \geq Grade 3 (using CTCAE, version 4.03), except as noted below:

- Grade \geq 3 skin toxicity, with the patient allowed to continue at the discretion of the investigator;
- Nausea and vomiting will be considered stopping criteria if Grade 3 toxicity persists after optimal medical therapy.

Any hepatobiliary disorders of \geq Grade 2 (from CTCAE, version 4.03, pages 24 – 25) will be considered adequate stopping criteria. Note that laboratory measurements are included in a separate section of the CTCAE.

Changes in ALT, AST, and total bilirubin levels must meet one of the following criteria to be considered a DLT:

- ALT or AST $>$ 8X ULN
- ALT or AST $>$ 5X ULN for more than 2 weeks
- ALT or AST $>$ 3X ULN and (total bilirubin $>$ 2X ULN or INR $>$ 1.5)
 - (Repeat testing every 72 to 96 hours until transaminase levels are below three times the ULN for at least one week or patient withdraws consent.)
- ALT or AST $>$ 3X ULN with the appearance of fatigue, nausea, vomiting, right upper quadrant pain or tenderness, fever, rash, and/or eosinophilia ($>5\%$)
 - (Repeat testing every 72 to 96 hours until transaminase levels are below three times the ULN for at least one week or patient withdraws consent.)

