#### **3.7.2 Definition of Study Baseline**

Unless otherwise noted, study baseline is defined as the last observation obtained prior to administration of the first dose on Study Day 1.

Change from baseline is defined as post-baseline assessment minus baseline assessment. The baseline value will not be used to impute the post-baseline values.

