#### 7.1.3 Treatment-Emergent Adverse Events

##### 7.1.3.1 Definition of Treatment-Emergent

Treatment-emergent adverse events are events that either:

- Date of onset on or after the date of the date of first dose and not more than 30 days after the date of the last dose of study drug, or
- Had no recorded date of onset with a stop date after the first dose of study drug, or
- Had no recorded date of onset or stop date

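### Treatment-emergent laboratory abnormalities are cut off at the last dose, while adverse events run 30 days longer and a full panel is drawn about 4 weeks after dosing ends

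*SAP*

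**What the plan says.** SAP 7.2.4 counts a laboratory value as treatment-emergent if it shows "any shift from a normal at baseline (Day 1) to abnormal at any time post-baseline up to and including the last dosing date", or if it moves from low at baseline to high afterwards, or the reverse. It adds: "If the relevant baseline laboratory values are missing, then any abnormality will be considered treatment emergent".

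The neighbouring sections use other limits:

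- **Adverse events (SAP 7.1.3.1):** onset on or after the first dose and "not more than 30 days after the date of the last dose of study drug".
- **Safety data in general (SAP 7):** everything from the first dose to the end of the study is summarized.
- **Laboratory summaries (SAP 7.2 and 7.2.5):** by-visit results, the change to the worst post-baseline value including unscheduled visits (where appropriate), by-visit Normal/Low/High counts, the treatment-emergent shift by visit, and the shift to the most abnormal value.

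The laboratory baseline has its own definition in SAP 7.2: "A baseline value is defined as the last available measurement obtained prior to administration of the first dose". SAP 3.7.2 agrees: "study baseline is defined as the last observation obtained prior to administration of the first dose on Study Day 1".

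The schedule of assessments (Protocol Table 3, SAP Appendix 1) places chemistry, hematology and urinalysis at screening, during radiation, on its last day, at Visit 11 (end of study drug) and at Visit 12, about 4 weeks after the final application. Neither Visit 2 (first dose) nor Visit 3 (first radiation) has a panel. Patients who stop lotion early are still asked to attend all visits (Protocol 8.4.1, SAP 1.2.2).

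**The concern.** Safety is one of the two primary objectives, and the treatment-emergent shift is the laboratory display that separates new abnormalities from those already present. The adverse event and laboratory tables use the same term with different end dates. An ALT that first rises at Visit 12 and is reported as an adverse event would count as treatment-emergent in one table and could not count in the other. The SAP gives no reason for the difference.

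A structural zero is also easy to misread. SAP 7.2.5 tabulates the treatment-emergent shift by visit, so the Visit 12 entry would show none for patients dosed to Visit 11, possibly beside non-zero High or Low counts on the same page. A reader could take that as reassurance.

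The adverse event table is not a full substitute. Under Protocol 12.6 a laboratory change becomes an adverse event only if judged clinically significant. Late liver and kidney findings deserve a clean table, because Protocol 5.1 names both as target organs in the 13-week rat dermal study.

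**Working it through.** The documents state no figure for this rule, so there is nothing to reproduce. The check compares the two windows with the schedule.

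**Step 1. Place each scheduled post-baseline chemistry draw against the two cut-offs.**

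| Draw | Days after last dose (full course) | Cut-off at last dose (7.2.4) | Cut-off at last dose + 30 (7.1.3.1) |
|---|---|---|---|
| During radiation | before last dose | inside | inside |
| Last day of radiation | before last dose | inside | inside |
| Visit 11, end of study drug | 0 | inside | inside |
| Visit 12, follow-up | about 28 | outside | inside |

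Outside under 7.2.4: 1/4 = 25%. Outside under the adverse event window: 0/4. With the ±2 day visit allowance, Visit 12 falls on day 28 − 2 = 26 to 28 + 2 = 30, so a visit within its allowance meets the 30-day limit. The position of the mid-radiation draw does not affect this count.

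**Step 2. Patients who depart from the full course.** For a patient who stops lotion early but keeps attending, every draw after the stop is outside. The cut-off also has no tolerance at Visit 11. Protocol 9.8.13 plans a final application that morning; if it is missed, the last dosing date falls before the visit, and 2 of 4 draws are outside.

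**Step 3. By-visit shift at Visit 12.** To be flagged, a value must be dated no later than the last dose. A patient dosed to Visit 11 has Visit 12 about 28 days after that date, so the flag cannot be set. The entry is zero by construction.

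**Step 4. How many patients could this touch?** The documents give no abnormality rate, so this is an illustration. Assume all 177 planned patients have a normal baseline and all four draws, each draw is abnormal with probability p, and draws are independent.

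- Abnormal only at follow-up: (1 − p)³ × p
- Abnormal at least once: 1 − (1 − p)⁴

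| p (assumed) | Only at follow-up | Expected of 177 | Ever abnormal | Share seen only at follow-up |
|---|---|---|---|---|
| 2% | 0.98³ × 0.02 = 0.0188 | 3.3 | 0.0776 | 24% |
| 5% | 0.95³ × 0.05 = 0.0429 | 7.6 | 0.1855 | 23% |
| 10% | 0.90³ × 0.10 = 0.0729 | 12.9 | 0.3439 | 21% |

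These are per test. Abnormalities that begin on treatment and persist would lower the share; effects that appear late would raise it.

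**Step 5. Baseline label.** SAP 3.7.1 makes Day 1 the first-dose date, while SAP 1.2.4 attaches Day 1 to the start of radiation. No panel is scheduled on either day. The pre-dose sample is the screening one, which "should be drawn ≤ 14 days prior to randomization in order to have current values for inclusion/exclusion assessment". The label therefore matches no planned draw, but the SAP 7.2 definition does match one.

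**The case against.** The strongest reply is that only a label is restricted. Values after the last dose still enter the by-visit summaries, the worst post-baseline change, the shift to most abnormal and the patient listings, none of which carries a stated on-treatment limit. Clinically significant changes can also be adverse events. An on-treatment laboratory window is a permissible choice, and the panel at Visit 11 supplies an end-of-treatment value. All of this is correct, and it limits the size of the point. It does not explain why one term has two end dates in the same safety section, or remove the structural zero at Visit 12.

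A reader might go further and infer three things that the documents do not support.

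- **That liver findings after dosing are dropped.** They lose the treatment-emergent flag only; the displays above keep them.
- **That a patient taken off lotion for a rising ALT has her peak removed.** Protocol 8.4.1 does require "Repeat testing every 72 to 96 hours until transaminase levels are below three times the ULN" in some cases, and those repeats may fall after the last dose. But the flag is a shift in category and carries no peak value. The transaminase thresholds in 8.4.1 all start above 3 times ULN, and the sample that prompts stopping would ordinarily be drawn while she is still dosing. With a normal baseline she is already flagged. The peak belongs to the worst post-baseline summary.
- **That no patient has a baseline, so every abnormality counts as new.** This needs a literal reading of the Day 1 label against SAP 7.2 and 3.7.2. Screening values must exist for the eligibility tests ("Have adequate hematologic and organ function at screening as follows"), so the missing-baseline sentence is not triggered across the trial.

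**Conclusion.** The window mismatch stands. Under SAP 7.2.4 an abnormality first seen at follow-up, or after early discontinuation, can never be called treatment-emergent, although an adverse event with the same onset could be up to 30 days after the last dose. The size is 1 of 4 scheduled post-baseline chemistry draws for patients who complete dosing, and every later draw for those who stop early. That is a count of draws and does not measure missed signals. The patient numbers in the working rest on assumed rates and independent draws.

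The Day 1 label is loose wording and would matter only if programmed literally. Overall the point is minor to moderate: it changes one safety table serving a primary objective and leaves the efficacy analysis as it is.

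**What to change.** In SAP 7.2.4, change the end of the window from the last dosing date to 30 days after the last dose, matching 7.1.3.1. As a clean-up in the same sentence, replace the Day 1 label with a reference to the SAP 7.2 baseline, the last measurement before the first dose. Unscheduled samples need no new text, because 7.2.4 does not restrict the flag to scheduled visits.

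The cost is two phrases, changed before database lock, with no new data. Counts of treatment-emergent abnormalities may rise slightly. A follow-up panel drawn later than day 30 would still be outside, but the laboratory and adverse event tables would then share the same limit.

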### 7.2.5 Summaries of Laboratory Abnormalities

The number and percentage of patients with laboratory normality and abnormality categories (Normal, Low, High) as well as the treatment-emergent shift will be summarized by treatment, laboratory category (hematology, chemistry, and urinalysis), test, and study visit. In addition to

by-visit frequencies, the most abnormal (low or high separately) as well as the shift to most abnormal (low or high) will be summarized.

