1.7 hr* μ g/mL were also not associated with any adverse findings, and thus, the NOAEL was also 8% RTA 408 Lotion. In the 13-week rat dermal GLP toxicity study, systemic exposures exceeded those associated with adverse effects in chronic oral toxicity studies in rats (*i.e.*, 4.6 hr* μ g/mL in the 13-week dermal study vs. 2.3 hr* μ g/mL in the 6-month oral dosing study). The liver and kidney were identified as target organs in the 13-week rat dermal GLP toxicity study, consistent with findings from the oral toxicity studies, and the resulting NOAELs were 0.3% RTA 408 Lotion in females and < 0.3% RTA 408 Lotion in males. Furthermore, the systemic toxicity potential of RTA 408 has been extensively studied in rats and monkeys, with daily oral administration for up to six months in rats and nine months in monkeys. Overall, based on an integrated assessment of the nonclinical data, and based on the demonstrated low systemic exposure to RTA 408 in healthy human volunteers after topical administration, it is concluded that RTA 408 Lotion has an acceptable safety profile for topical use as indicated in this Phase 2 study in female patients at risk for radiation dermatitis.

A Phase 1 study (408-C-1305) was completed to evaluate the safety, local pharmacodynamics (PD), and systemic pharmacokinetics (PK) of RTA 408 following topical application of RTA 408 Lotion to healthy volunteers. The Phase 1 study was conducted in three parts. In Part A of the study, RTA 408 Lotion Vehicle and RTA 408 Lotion (0.5%, 1%, and 3%) were each concurrently applied to a small skin surface area (four individual 4-cm² sites; 16 cm² total area) twice daily for 14 days. The maximum tolerated drug concentration in Part A was 3% RTA 408 Lotion. In Part B, RTA 408 Lotion (3%) was applied topically twice daily for 14 days to a larger skin surface area (~100 cm²). In Part C, 3% RTA 408 Lotion was applied topically twice daily for 28 days to an even larger skin surface area (~500 cm²). Approximately 32 healthy adult volunteers were enrolled in the Phase 1 study with 12 volunteers in Part A, 10 volunteers in Part B, and 10 volunteers in Part C.

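### No planned laboratory table counts patients who pass the protocol's own liver limits, and worsening in an already abnormal direction is never treatment-emergent

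*SAP*

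**What the plan says.** SAP 7.2.5 will summarize by arm "The number and percentage of patients with laboratory normality and abnormality categories (Normal, Low, High) as well as the treatment-emergent shift", and further by laboratory category, test and visit. The same section adds that "the most abnormal (low or high separately) as well as the shift to most abnormal (low or high) will be summarized". The abnormality flags come from the central laboratory (SAP 7.2.3).

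SAP 7.2.4 defines a treatment-emergent laboratory abnormality as "any shift from a normal at baseline (Day 1) to abnormal at any time post-baseline up to and including the last dosing date". It adds two further routes: a move from low to high or the reverse, and any abnormality when the baseline value is missing.

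Other laboratory outputs are planned. They are continuous summaries with change from baseline for selected hematology and chemistry tests (SAP 7.2.2), change to the worst post-baseline value where judged appropriate (SAP 7.2), and listings by patient (SAP 7.2.1).

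Protocol 8.4.1 states: "Changes in ALT, AST, and total bilirubin levels must meet one of the following criteria to be considered a DLT". Four limits follow:
- ALT or AST above 8 times ULN;
- ALT or AST above 5 times ULN, lasting over 2 weeks;
- ALT or AST above 3 times ULN with bilirubin above 2 times ULN or INR above 1.5;
- ALT or AST above 3 times ULN with listed symptoms or eosinophilia.

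On entry, Protocol 8.1 allows bilirubin up to 1.5 times ULN and requires ALT and AST no higher than ULN. The Protocol synopsis allows up to 2 times ULN for all three.

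**The concern.** Safety is one of the two primary objectives (Protocol 6.1). The background section reports that "The liver and kidney were identified as target organs in the 13-week rat dermal GLP toxicity study". The protocol therefore defines a liver signal by how far a value rises and by what rises with it, but the SAP's abnormality tables record neither. Once a value crosses ULN, the High cell says nothing more about it. A patient who starts above ULN and goes higher is left out of the treatment-emergent count altogether.

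A reader of the study report would want to know how many patients in each arm passed each limit in 8.4.1. No planned table answers that. The answer would have to be assembled by hand from listings, or inferred from adverse event tables that depend on what investigators chose to report.

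**Working it through.** The plan gives no figure to reproduce. The check applies the SAP's classification rules to example values and compares the results with the protocol's limits. The example values and event rates are assumptions.

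**Inputs from the documents.** Classes Normal/Low/High (SAP 7.2.5); the three treatment-emergent routes (SAP 7.2.4); limits of 3, 5 and 8 times ULN for ALT/AST and 2 times ULN for bilirubin (Protocol 8.4.1); entry limits (Protocol 8.1 and synopsis); 59 patients per arm, so 118 on active lotion (Protocol 7.2).

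**Rule, high side.** With x = value/ULN, the class is High if x > 1 and otherwise Normal. With a baseline present, a high value is treatment-emergent only if the baseline was Normal (or Low).

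| Assumed path (x ULN) | Shift in 7.2.5 | Treatment-emergent in 7.2.4 | Protocol limit passed |
|---|---|---|---|
| ALT 0.8 to 1.05 | Normal to High | yes | none |
| ALT 0.8 to 3.5 | Normal to High | yes | >3 |
| ALT 0.8 to 5.5 | Normal to High | yes | >3, >5 |
| ALT 0.8 to 8.5 | Normal to High | yes | >3, >5, >8 |
| ALT 1.2 to 8.5 (synopsis entry limit only) | High to High | no | >3, >5, >8 |
| ALT 1.9 to 8.5 (synopsis entry limit only) | High to High | no | >3, >5, >8 |
| Bilirubin 1.4 to 2.5 (allowed by 8.1) | High to High | no | >2, the bilirubin part of the combined limit |

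The first four rows cannot be told apart in the abnormality and shift tables. The last three are not treatment-emergent.

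**Two tests in one patient.** Suppose bilirubin goes from 1.2 to 2.5 times ULN while ALT goes from normal to 4 times ULN. She meets the combined limit (4 > 3 and 2.5 > 2). The tables show a treatment-emergent High ALT in one place and a High-to-High bilirubin in another. Nothing shows that they belong to the same patient.

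**Counts by arm.** Six patients at 1.1 to 1.5 times ULN on vehicle and six above 5 times ULN on 3% lotion would both read 6/59 = 10.2% High.

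**Continuous tables.** One patient going from 0.8 to 8.5 times ULN moves an arm's mean change by (8.5 − 0.8)/59 = 0.13 times ULN, or by 7.7/118 = 0.07 in the pooled active arms. Only the maximum would show her, and the SAP does not say that it will be expressed against ULN.

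**After the fix.** Rows for >3, >5 and >8 times ULN separate the first four paths and count the two 8.5 paths whatever the baseline. The chance of at least one case is 1 − (1 − p)^n:

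| True rate p | n = 59 | n = 118 |
|---|---|---|
| 1% | 45% | 69% |
| 2% | 70% | 91% |
| 3% | 83% | 97% |
| 5% | 95% | 99.8% |

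At these rates an arm of 59 would be expected to yield between 59 × 0.01 = 0.6 and 59 × 0.05 = 3 cases. With numbers that small, a patient count is informative and a mean is not.

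**The case against.** The strongest reply is that the SAP offers more than these tables, and much of it stands.

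- A reader might infer that all laboratory safety output is reduced to three classes. It is not: continuous summaries, change to worst value and listings are planned. In the six-against-six example, take a baseline of 0.8, peaks of 5.5 and 1.3, and no change in the other patients. The mean change to worst would then be 6 × 4.7/59 = 0.48 times ULN against 6 × 0.5/59 = 0.05, with very different maxima. If that table is produced, such a contrast would be visible. However, the table is conditional, takes one test at a time and counts no patients. The by-visit summaries use scheduled values only, so they leave out unscheduled repeat tests.
- A reader might infer that only shifts from normal are treatment-emergent. SAP 7.2.4 also counts low-to-high, high-to-low and missing-baseline cases. The gap is confined to worsening in the same direction.
- A reader might infer that the two-test patient's bilirubin disappears. It still appears as High by visit and in the most-abnormal and shift tables. Only the treatment-emergent flag and the link to ALT are missing.
- Patients past a limit may appear in tables of adverse events by severity, serious events, events leading to discontinuation, or reasons for stopping treatment (SAP 4.1 and 7.1.6.1). This is a real route, but under Protocol 12.6 a laboratory change becomes an adverse event only if judged clinically significant.
- The target-organ finding comes from rats at 4.6 hr*µg/mL. The 13-week minipig study had no adverse findings, and the only measurable human AUC in Phase 1 was 0.0019, about 2,400 times lower (4.6/0.0019). This makes a liver signal less likely. It does not remove the reason to report against limits that the protocol itself set.
- Under Protocol 8.1, ALT and AST cannot enter above ULN. The documents also give no support for saying that patients with raised baselines are at greatest risk.

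**Conclusion.** The point holds in a limited form. The abnormality and shift tables cannot separate a trivial rise from one past the limits in Protocol 8.4.1, same-direction worsening is not treatment-emergent, and no planned table gives by-arm counts against those limits or joins ALT/AST with bilirubin within a patient. The documents do not support the stronger inference that a liver signal would be hidden, because other outputs may reveal an extreme value.

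The raised-baseline part rests on bilirubin, which Protocol 8.1 admits up to 1.5 times ULN. It extends to ALT and AST only under the synopsis limit. The two entry limits conflict and must be reconciled, since they decide how many patients can start high. On the low side, entry allows hemoglobin down to 9 g/dL and platelets just above 100 × 10^9/L. Further falls would go uncounted if those values lie below the laboratory's normal range, which the documents do not give.

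Neither the primary efficacy analysis nor data collection is affected. This is a cheap improvement to the reporting of a primary safety objective.

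**What to change.** In SAP 7.2.5, add a table by arm, regardless of baseline and including unscheduled post-baseline values, of patients with:
- peak ALT or AST above 3, above 5 and above 8 times ULN;
- ALT or AST above 3 times ULN together with total bilirubin above 2 times ULN in the same patient;
- ALT or AST above 5 times ULN for more than 2 weeks, derived from serial values, because a single worst value cannot show duration.

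Report the INR alternative only if INR was measured; it is in no listed panel (Protocol 9.8.16 and 9.8.17, SAP Appendix 2). Report the symptom limit only by linking laboratory and adverse event data. State the table's time window, because SAP 7.2.4 stops at the last dosing date and laboratory samples are also taken at follow-up.

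In SAP 7.2.4, also count worsening in the same direction from an abnormal baseline. Use ULN-multiple categories for ALT, AST and bilirubin, since 8.4.1 bases its transaminase criteria on FDA guidance rather than CTCAE. Use CTCAE v4.03 grade for creatinine, hemoglobin, neutrophils and platelets.

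The cost is SAP wording, one or two more tables, some programming for the duration rule and any adverse event link, and slightly higher treatment-emergent counts. The change affects reporting only; no stopping rule or entry limit is altered.
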